5.3 DRUG CONCENTRATION MEASUREMENTS AND PHARMACOKINETICS

Not applicable

5.4 ASSESSMENT OF BIOMARKER(S)

No exploratory biomarkers are planned. Established biomarkers of efficacy and safety are described and discussed in [Sections 5.1](#) and [5.2](#).

5.5 BIOBANKING

Not applicable

5.6 OTHER ASSESSMENTS

Not applicable

5.7 APPROPRIATENESS OF MEASUREMENTS

The primary endpoint measurements will be consistent with the recognized standard for patients hospitalised with SARS-CoV-2.

All other measurements performed during this trial are standard measurements and will be performed in order to determine the efficacy and safety in an appropriate way.

Therefore, all measurements performed in this trial are considered by the sponsor to be appropriate.

6. INVESTIGATIONAL PLAN

6.1 VISIT SCHEDULE

The visit schedule is to be adhered to as specified in the [Flow Chart](#). Each visit date (with its window) is to be counted from Day 1.

If any visits cannot be performed while the patient is hospitalised, subsequent visits should follow the original visit date schedule. Blood sampling for safety laboratories and pregnancy testing is marked with a window of +/- 1 day in the [Flow Chart](#) and should be performed accordingly when a daily visit cannot be done.

If any Follow-up (FUP) visits have to be rescheduled, subsequent visits should follow the original visit date schedule.

Additional visits for the purpose of re-testing of laboratory parameters or AE monitoring may be included as deemed necessary by the investigator.

6.2 DETAILS OF TRIAL PROCEDURES AT SELECTED VISITS

Study procedures to be performed at each visit are listed in the [Flow Chart](#) and explanations provided in [Section 5](#). Additional details on procedures at selected visits are provided below.

At all applicable visits vital signs, blood gases and WHO Clinical Progression Scale assessment should be done prior to study drug administration.

6.2.1 Screening and run-in period(s)

Screening Period

The Screening period is defined as the period from the screening visit to randomization (first study drug administration).

All patients (or the patient's legally accepted representative) must sign an Informed Consent consistent with ICH-GCP guidelines and the local legislation prior to any study specific procedures (refer to [Section 8.1](#)). Once consented, the patient is considered to be enrolled in the trial and have started screening. The patient should be recorded on the enrolment log and registered in IRT as a screened patient. Patients will be assigned a patient number and enrolment must be recorded in eCRF pages.

Patients who do not meet eligibility criteria should be documented as a screen failure. Rescreening will not be permitted. Procedures can be retested as necessary per investigator judgement to confirm eligibility prior to randomization.

If a patient is enrolled in error (does not meet all inclusion criteria or meets one or more exclusion criteria on the day of enrolment), the sponsor should be contacted immediately.

Medical History:

Medical history includes estimated date and time of first SARS-CoV-2 infection symptoms as well as symptom details.

Baseline Conditions:

Baseline conditions include number of co-morbidities (e.g., respiratory, cardiovascular, metabolic, malignancy, endocrine, gastrointestinal, immunologic, and renal).

6.2.2 Treatment period(s)

The treatment period starts with Visit 2 (Day 1, randomization) and ends with the EOT visit (possible Day 2 through Day 29). Patients will remain hospitalised during the treatment period and daily protocol visits will be conducted to complete procedures according the [Flow Chart](#). Patients may receive treatment with study drug for up to 28 days, however if a patient is well enough to be discharged, then study drug may be stopped before the maximum treatment duration (i.e. 28 days).

EOT visit should be completed the day after the last dose of study drug is administered for all patients regardless of discharge status. EOT visit is expected to align with day of discharge, unless it is planned for a patient to remain hospitalised after treatment with study drug is stopped. EOT visit should occur no later than Day 29.

6.2.3 Follow-up period and trial completion

For all randomised patients, termination of trial medication and trial completion must be recorded on the corresponding eCRFs.

Applicable FUP visits and EOS visits will be conducted remotely by a phone contact for all patients that have completed treatment, EOT visit, and discharge. Each of these visits includes vital status.

FUP visits should be conducted as follows:

- FUP 1 should be performed 4 days after EOT visit for all patients.
- FUP 2 and FUP 3 which correspond to study Day 15 and Day 29 after start of therapy, should be performed *if the time point is applicable after drug discontinuation*. FUP 2 and FUP 3 visits should not be conducted within +/- 2 days of EOT or FUP 1.
- FUP 4 and EOS which correspond to study Day 60 and Day 90 will be performed for all patients.

If a patient remains hospitalized after EOT visit, applicable FUP visits and the EOS visit will be conducted in hospital until discharge and thereafter by telephone.

If a patient withdraws participation from the study, it may be agreed to collect vital status per the remaining originally planned visit schedule according to the [Flow Chart](#).

Trial completion is defined as patients completing the FUP and EOS visits according to the [Flow Chart](#).

7. STATISTICAL METHODS AND DETERMINATION OF SAMPLE SIZE

This is a randomized, double-blind, placebo-controlled, parallel group trial with an anticipated treatment period of 4 week and a follow up period of up to 90 days from randomisation. BI 764198 will be compared to placebo in hospitalised patients at risk of developing ARDS or diagnosed with ARDS secondary to COVID-19 infection.

The primary endpoint is patients alive and free of mechanical ventilation at Day 29 and will be analysed using a logistic regression model to compare the absolute difference in proportions of patients alive and free of mechanical ventilation at Day 29 with BI 764198 and placebo. Detailed specifications are provided in [Section 7.2.2](#).

The primary endpoint and secondary endpoints are defined in [Section 2.1](#).

7.1 NULL AND ALTERNATIVE HYPOTHESES

No formal testing will be performed and hence no null and alternative hypotheses are defined since this is an exploratory study.

7.2 PLANNED ANALYSES

7.2.1 General considerations

The efficacy analysis will be performed in all randomized patients who documented to have received at least one dose of trial medication. This set will be called Full Analysis Set (FAS).

Patients will be analysed as randomised, without regard to any treatment changes. The intent-to-treat (ITT) principle will be applied to the randomized set including all observed data in the primary analysis regardless of treatment discontinuation. Baseline refers to the last measurement prior to randomisation.

7.2.2 Primary endpoint analyses

To evaluate the difference in proportions of patients alive and free of mechanical ventilation at Day 29 with BI 764198 and placebo, the analysis of the primary endpoint will be performed with a logistic regression model including covariates of treatment, severity grade at baseline, age, creatinine at baseline, and duration of symptoms before hospitalisation. The point estimates, standard errors and confidence intervals for the difference in proportions will be derived based on the estimates from the logistic regression model. Patients who terminate the study medication prematurely will be followed and the events which occur after premature discontinuation of medication and before the time point of interest will be included in the analysis using Full Analysis Set (FAS). Patients will be analysed according to their assessed severity grade on the WHO Clinical Progression Scale recorded at baseline (last assessment prior to administration of study drug).

A sensitivity analysis will be conducted with a logistic regression model including covariates of treatment, severity grade at baseline, age, creatinine at baseline, D-dimer at baseline, and duration of symptoms before hospitalisation with patients who don't miss D-dimer at baseline. Details will be defined in TSAP.

Subgroup analysis will be performed using descriptive statistics/figures by subgroup e.g., age category, race, baseline severity grade, categorized duration of symptoms before hospitalisation, etc. Details will be defined in TSAP.

7.2.3 Secondary endpoint analyses

Analysis of patients alive and discharged free of oxygen at Day 29 and mortality at Day 15, 29, 60, and 90 will be conducted using the same model used for the primary endpoint, to assess the difference in proportions of patients with BI 764198 and placebo .

The difference of ventilator free days between BI 764198 and placebo group will be analysed using an ANCOVA model including treatment, age, creatinine at baseline, and duration of symptoms before hospitalisation.

Time to response, defined as clinical improvement of at least 2 points (from randomisation) on the World Health Organization Clinical Progression Scale, discharge from the hospital, or considered fit for discharge (a score of 0, 1, 2, or 3 on the Clinical Progression Scale), whichever comes first, by Day 29, will be analysed using a Cox proportional-hazards model including covariates of treatment, age, creatinine at baseline, and duration of symptoms before hospitalisation will be performed. Hazard ratio and Kaplan-Meier curves will be provided. Patients who do not respond will be censored at Day 29.

[REDACTED]

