| Comparator product(s) | Placebo to BI 764198 |
| dose | Not applicable |
| mode of administration | Oral (p.o.) or, only if needed, nasogastric intubation |
| Duration of treatment | Up to 28 days |
| Statistical methods | 
The primary endpoint will be analysed with a logistic regression model using covariates of treatment, severity grade at baseline, age, creatinine at baseline, and duration of symptoms before hospitalisation, to evaluate the absolute difference in proportions of patients alive and free of mechanical ventilation at Day 29 with BI 764198 and placebo. Patients who terminate the study medication prematurely will be followed and the events which occur after premature discontinuation of medication and before the time point of interest will be included in the analysis using the Full Analysis Set (FAS).
 
The logistic regression for the primary endpoint analysis will be used for other binary endpoint(s) and time-to-event endpoints will be analysed using Cox regression including covariates used for the primary analysis. Ventilator free days will be analysed using ANCOVA including the same covariates as in the primary analysis.
 |

FLOW CHART

| Trial Periods | Screening | Treatment | | | Follow-up (telephone visits only ^b) | | |
|--|----------------------|---------------|---------------------------|---|--|-----------------------|-----------------------------|
| | | 1 | 2 | 3 through 29 | EOT ^a | FUP ^b 1 | FUP ^b 2, 3, 4 |
| Visit | | | | | | | |
| Day | -1 | 1 | | Daily Day 2 through discharge -1 day (maximum Day 28) | discharge/ day after last dose | EOT +4 days | 15, 29, 60 (from Day 1) |
| Time window for visits (days) | -3 to 1 ^c | | | | | +2 | ±3 |
| Informed Consent | X | | | | | | |
| Demographics | X | | | | | | |
| Medical History | X | | | | | | |
| Baseline Conditions | X | | | | | | |
| Clinical Frailty Scale (CFS) | X | | | | | | |
| SARS-CoV-2 PCR test ^{c,h} | X | | | | | | |
| Review of inclusion/exclusion criteria ^c | X | X | | | | | |
| Randomisation | | X | | | | | |
| Concomitant Therapy and Procedures | X | X | X | X | X | X | X |
| Adverse event evaluation | X | X | X | X | X | X | X |
| Hospitalisation Status | X | X | X | X | X | X | X |
| World Health Organization (WHO) Clinical Progression Scale | X | X | X | X | X ^f | X ^f | |
| Ventilation and oxygen parameters; respiratory rate, FiO ₂ , SpO ₂ | X | X | X | X | X ^f | X ^f | |
| Vital signs (refer to Section 5.2.2) | X | X | X | X | | | |

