### **3. INTRODUCTION**

As per ICH E9 ill, the purpose of this document is to provide a more technical and detailed elaboration of the principal features of the analysis described in the protocol, and to include detailed procedures for executing the statistical analysis of the primary and secondary variables and other data.

This TSAP assumes familiarity with the Clinical Trial Protocol (CTP), including Protocol Amendments. In particular, the TSAP is based on the planned analysis specification as written in CTP Section 7 "Statistical Methods and Determination of Sample Size". Therefore, TSAP readers may consult the CTP for more background information on the study, e.g., on study objectives, study design and population, treatments, definition of measurements and variables, planning of sample size, randomization.

The trial data is stored in the BI Rave (BRAVE) database system.

S A S® Version 9.4 will be used for analyses.

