#### **7.5.2 (Other) Secondary endpoints**

Secondary endpoints will be analyzed on the FAS using treatment policy estimand.

Proprietary confidential information © 2021 Boehringer Ingelheim International GmbH or one or more of its affiliated companies

- Analysis of patients alive and discharged free of oxygen at Day 29 will be conducted using the same model as for the primary endpoint, to assess the difference in proportions of patients with BI 764198 and placebo.
- Analysis of patients with occurrence of any component of composite: In-hospital mortality or intensive care unit (ICU) admission or mechanical ventilation at Day 29, will be conducted using the same model used as the primary endpoint, to assess the difference in proportions of patients with BI 764198 and placebo.
- Time to response, defined as clinical improvement of at least 2 points (from randomisation) on the World Health Organization Clinical Progression Scale, discharge from the hospital, or considered fit for discharge (a score of 0, 1, 2, or 3 on the Clinical Progression Scale), whichever comes first, by Day 29, will be analysed using the Cox proportional-hazards model adjusting for treatment, age, creatinine at baseline, and duration of symptoms before hospitalisation. Hazard ratio and Kaplan-Meier curves with 95% confidence interval will be provided. Patients who do not respond will be censored at Day 29. Patients who prematurely discontinued from the treatment or lost to follow-up will be censored at the time of their last observed assessment. Patients who die prior to observing response will be censored at Day 29.
- The number of ventilator free days will be analysed using an ANCOVA model including treatment, age, creatinine at baseline, and duration of symptoms before hospitalisation. WHO progression scale below 7 are defined as ventilator free. Hence, ventilator free days can be counted as number of days with WHO progression scale below 7 from the day of randomization to day 29. A sensitivity analysis excluding patients who died during treatment period will be conducted.
- Analysis of mortality at Day 15, 29, 60 and 90 will be conducted using the same model as for the primary endpoint, to assess the difference in proportions of patients with BI 764198 and placebo.

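### Baseline WHO grade, the only stratification factor, is missing from the Cox and ventilator-free-days models in Protocol 7.2.3 and SAP 7.5.2, contrary to the protocol synopsis

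*Protocol*

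**What the plan says.** The synopsis (Statistical methods) states that "time-to-event endpoints will be analysed using Cox regression including covariates used for the primary analysis" and that "Ventilator free days will be analysed using ANCOVA including the same covariates as in the primary analysis". Protocol 7.2.2 defines the primary analysis as a "logistic regression model including covariates of treatment, severity grade at baseline, age, creatinine at baseline, and duration of symptoms before hospitalisation".

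Protocol 7.2.3 gives shorter lists. Time to response gets a "Cox proportional-hazards model including covariates of treatment, age, creatinine at baseline, and duration of symptoms before hospitalisation", and ventilator-free days get an "ANCOVA model including treatment, age, creatinine at baseline, and duration of symptoms before hospitalisation". SAP 7.5.2 follows suit with a "Cox proportional-hazards model adjusting for treatment, age, creatinine at baseline, and duration of symptoms before hospitalisation", and for the other endpoint: "The number of ventilator free days will be analysed using an ANCOVA model including treatment, age, creatinine at baseline", followed by symptom duration. The SAP introduction says that "the TSAP is based on the planned analysis specification as written in CTP Section 7", and SAP Section 4 declares no change to the planned analysis.

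Protocol 3.1 and 7.4 stratify randomisation by baseline grade, 5 against 6, and name no other factor.

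**The concern.** The current protocol describes two models for each of two secondary endpoints, one with severity grade and one without. The SAP carries the version without it and does not mention the conflict.

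The missing term is the one the design singles out. Allocation is balanced within grade, so an analysis that ignores grade does not use the balance the randomisation created. Elsewhere the plan does use it: grade is in the primary model, in the binary secondary analyses that borrow that model, and in every logistic sensitivity model in SAP 7.4.1, and it supplies the weights of the Cochran-Mantel-Haenszel analysis. Only the Cox and ventilator-free-days models lack it.

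If grade is prognostic, the Cox hazard ratio is pulled toward 1 relative to the value within grade, and the ANCOVA reports an interval wider than its estimate deserves. For a trial whose stated aim (Protocol 2.1.1) is to estimate the treatment effect, that is a loss even without formal testing.

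**Working it through.** **1. Covariate lists side by side**

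| Source | Treatment | Grade | Age | Creatinine | Symptom duration |
|---|---|---|---|---|---|
| Primary model (Synopsis, Protocol 7.2.2, SAP 7.4.1) | yes | yes | yes | yes | yes |
| Cox and ANCOVA, Synopsis | yes | yes (by reference) | yes | yes | yes |
| Cox and ANCOVA, Protocol 7.2.3 | yes | **no** | yes | yes | yes |
| Cox and ANCOVA, SAP 7.5.2 | yes | **no** | yes | yes | yes |

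The lists differ by exactly one term. The plan states no figure to reproduce, so the rest sizes the consequence.

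**2. Inputs.** From the documents: 130 patients, 1:1, blocked within grade. Assumed, because the documents do not give them: share of Grade 6, prognostic effect of grade, response times, treatment effect and block size.

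**3. Cox model.** Simulation with 4,000 trials per scenario, blocks of 4 within grade, 40% Grade 6, exponential response times, Grade 5 placebo median 8 days, censoring at 28 days, treatment hazard ratio 1.6, and no deaths or other covariates. Chance that the Wald 95% interval excludes 1:

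| Grade 6 vs 5 hazard ratio for response | Grade omitted | Grade included | Loss (points) |
|---|---|---|---|
| 1.0 | 73.9% | 74.1% | 0.2 |
| 0.8 | 69.8% | 70.9% | 1.1 |
| 0.7 | 70.1% | 71.8% | 1.7 |
| 0.6 | 68.2% | 72.0% | 3.8 |
| 0.5 | 64.5% | 70.2% | 5.7 |
| 0.4 | 58.5% | 68.9% | 10.4 |
| 0.3 | 49.2% | 66.7% | 17.5 |

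- With 20% Grade 6, the loss is 0 to 2 points at 0.7 or weaker, 9 at 0.4 and 14 at 0.3.
- Estimated treatment hazard ratio, omitted vs included: 1.59 vs 1.61 at a grade hazard ratio of 0.7, and 1.47 vs 1.61 at 0.3.
- The reported standard error of the log hazard ratio barely changes (0.192 vs 0.194 at 0.4), so the loss does not come from a wider interval; it comes with the shift of the estimate toward 1.
- With no treatment effect and a grade hazard ratio of 0.4, the interval excludes 1 in 3.5% of trials (omitted) vs 5.1% (included).
- Slower response (daily hazard 0.07 in Grade 5 on placebo, median ln 2/0.07 = 9.9 days; 3,000 trials) gives the same picture: 69% vs 71% at 0.7, 62% vs 68% at 0.5, 48% vs 65% at 0.3.

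**4. ANCOVA.** With treatment balanced within grade, the ratio of reported standard errors (omitted to included) is 1/√(1 − R²), where R² is the share of residual variance that grade explains.

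- R² = 5%: 1/√0.95 = 1.026
- R² = 15%: 1/√0.85 = 1.085
- R² = 30%: 1/√0.70 = 1.195

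Simulation (4,000 trials each, Gaussian outcome, 40% Grade 6) gives ratios of 1.026, 1.085 and 1.197. The true standard deviation of the estimate is nearly the same with and without grade (0.1757 vs 0.1758, 0.1767 vs 0.1766, 0.1742 vs 0.1737), so the reported interval is simply too wide: coverage is 95.5%, 96.4% and 98.3% against a nominal 95%.

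To link R² to this endpoint, simplify ventilator-free days to 28 or 0, with failure rates p5 and p6. With 40% Grade 6, R² = 0.4 × 0.6 × (p6 − p5)² / [p̄(1 − p̄)], where p̄ = 0.6·p5 + 0.4·p6.

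- 20% / 30%: p̄ = 0.24; R² = 0.0024/0.1824 = 1.3%; SE 0.7% too large
- 15% / 40%: p̄ = 0.25; R² = 0.0150/0.1875 = 8.0%; SE about 4% too large
- 10% / 50%: p̄ = 0.26; R² = 0.0384/0.1924 = 20.0%; SE about 12% too large

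**The case against.** The detailed sections agree with each other. Protocol 7.2.3 and SAP 7.5.2 give one explicit list, and the SAP takes its specification from protocol Section 7, so a programmer following the SAP has one model per endpoint. On that reading only the synopsis is out of line and could be corrected instead. This stands in part: the documents do not show which version was intended. But aligning the synopsis would keep the less efficient model and the overwide ANCOVA interval, and a reason for the omission would still be needed.

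The impact is limited. Protocol 7.1 plans no formal testing, only two secondary endpoints are affected, and the errors are conservative. That stands.

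The large Cox losses need a strong grade effect. For time to response the effect may be weak, because a 2-point improvement takes a Grade 6 patient to Grade 4, still in hospital, but requires Grade 3 of a Grade 5 patient. The planned models also adjust for age, creatinine and symptom duration; where these correlate with grade they absorb part of its effect, so the simulated losses lean toward an upper bound. Both points stand.

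A hazard ratio not conditioned on grade is a different quantity, not merely a biased one. That is correct, and neither document says which is wanted. The lower chance of the interval excluding 1, and the under-sized 3.5% under no effect, do not depend on that choice.

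Finally, SAP Section 10, cited for SAS code, is not in the copy reviewed. The visible text of SAP 7.5.2 states no strata term.

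**Conclusion.** The point holds. That the synopsis and the detailed sections conflict is certain from the text. The statistical cost is conditional: close to nil if grade is weakly prognostic, and material for the Cox model only if the grade hazard ratio is about 0.5 or stronger. For ventilator-free days it is a few per cent on the standard error under moderate differences between grades. It rests on the assumed Grade 6 share, response times and effect sizes, and on leaving out deaths and the other covariates. The omission does not favour the drug and does not touch the primary analysis. It should be corrected because a known contradiction is left open and the remedy costs almost nothing.

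**What to change.** Add baseline WHO grade (5 vs 6) as a covariate to the Cox and ANCOVA models in Protocol 7.2.3 and SAP 7.5.2, using the assessed baseline grade as Protocol 7.2.2 already requires for the primary analysis. This brings both models into line with the synopsis and the randomisation. A Cox model stratified by grade may be added as a sensitivity analysis. If the sponsor keeps the shorter list, the synopsis must be corrected and the reason stated. Either way, settle it before treatment codes are released under SAP Section 8. The cost is wording in two sections and one term per model; grade is already collected and used for randomisation, so no further data are needed.
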